5.1.3 Professional Organizations and Healthcare Delivery Systems

Members of the research team and our panel of stakeholders are members of professional and clinical organizations, including the American Medical Association, American College of Surgeons, Society of Surgical Oncology, American Society of Breast Surgeons, American Society of Clinical Oncology, American College of Surgeons Diversity Issues Committee, International Patient Decision Aids Standards Collaboration, American College of Radiology Imaging Network, and Society for Medical Decision Making, among many others. We will disseminate our findings and successful intervention(s) to these influential professional organizations to inform practice recommendations and implement lasting changes in routine care. Further, Dartmouth-Hitchcock is part of the High Value Healthcare Collaborative, a consortium of 13 healthcare delivery systems across the United States. Communicating our findings to these healthcare systems will offer a direct opportunity for widespread dissemination, implementation, and impact.

5.1.5 Dissemination Symposia and Clinician Training Module

Lastly, we will organize a symposium at each participating study site. The dissemination symposia will be guided by patients and community stakeholders to disseminate knowledge locally, facilitate knowledge transfer at each site, and foster opportunities to disseminate the research findings nationally. We will also release a brief shared decision-making training module on our website that will be based on the training delivered to clinicians in the trial and are available to health professionals to implement the interventions in routine care. We will

also disseminate this training module using the professional organizations and healthcare delivery systems mentioned in section 5.1.3.

5.2 Possible Barriers to Dissemination and Implementation

We understand that one of the greatest challenges to implementing results in clinical settings is finding sustainable partnerships, where patient-centeredness is a priority. Partnerships with patient-groups, clinicians, and patients are essential, and we have therefore made considerable efforts to achieve these goals.

We have reached out to recognized leaders in the field of patient-centered care who focus on breast cancer care ([name], [name], [name], [name], [name] and [name]). We have also involved several patient and stakeholder partners who will be engaged in all aspects of the project, including its dissemination and implementation. We have designed the project around a representative sample of patients, which determined our choice of four geographically diverse sites by region and population. We will ensure that the findings are effectively disseminated at each site as well as nationally using the channels listed above.

Another clear barrier to disseminating findings to patients, clinicians, and non-academic audiences is the difficulty in communicating information in a way that is clear and meaningful to each stakeholder group. We will work closely with our patient partners and clinician stakeholder partners to produce reports, newsletters, and informative videos that are understandable and pertinent.

We also recognize that barriers to sustained implementation are often due to poor clinical engagement whereby research conducted in controlled settings finds limited use in routine care. From the outset, we have been mindful to maximize the implementation and dissemination potential of the study and interventions by continuously involving clinicians and patients in every aspect of the planned trial and development of both interventions. These tools have been demonstrated to be both feasible and acceptable to clinicians in routine care with minimal impact on the consultation length^{63,65,92}. Implementation will also depend on ensuring that our approach is flexible enough to be widely applicable across diverse settings and within diverse communities. This is why we will take great care to translate interventions and measures into Spanish and Mandarin Chinese and have pilot-tested them with patients from various SES, ethnic, and racial backgrounds.

[figure not shown]
5.3 Making Results Available to Participants

As described above, we will produce a study report in collaboration with our patient and stakeholder partners and share it with all participants after study completion. The report will also be freely available to all on the study website. Further, our dissemination plan also includes organizing a local research symposium at each participating study site as a way to “meet patients and stakeholders in their own communities” and showcase findings. The PI has experience of organizing patient/stakeholder-led symposia to promote knowledge translation and disseminate research findings. These events have been shown to have a significant impact on the entire community with repercussions nationally.

6 Timeline

The study will last 36 months, starting on November 1, 2016. See Gantt Chart below for a detailed timeline.

Figure 7. Study Timeline

The following milestones will be achieved:

Table 5. Study Milestones

	Milestone Name	Description	Projected Completion Date
A	Effective Date	Start of contract award	11/1/16
B1	Study team meeting	First study team meeting (monthly thereafter until study completion)	11/1/16
B2	Community Advisory Board Meeting	First community advisory board (CAB) meeting, which will include patient and stakeholder partners (held quarterly until study completion) - submitt CAB meeting minutes with interim progress reports.	1/31/17
B3	Protocol Complete	Final trial protocol completed	2/28/17
B4	IRB Approval Obtained	Obtain IRB Approval(s) for study and submit approval letter(s) to PCORI.	2/28/17
B5	Select and register project at appropriate site for the study design (Clinicaltrials.gov, RoPR, or other as approved by PCORI before study start date)	Study Identification Number and the Primary Research Completion Date must be sent to PCORI.	2/28/17
B6	Study website	Study website launched	2/28/17
B7	Steering Committee Meeting	First trial Steering Committee meeting (held quarterly until study completion) - submit meeting minutes with interim progress reports.	2/28/17
B8	DSMB meeting	DSMB meeting (occurs every six months until study completion) - submit meeting minutes with interim progress reports.	4/30/17
B9	Engagement Update	For the 6-month time intervals (i.e., 6 months, 18 months, 30 months, etc. but not at 12 months or 24 months), provide specific examples of the impact of engagement on project activities during the reporting	5/1/17

		period. Report this in the Engagement Report section of the PCORI interim progress report.	
B	Progress Report Submission	Submit 6-month Interim Progress Report - use PCORI interim progress report template	5/1/17
C1	DQI adaptation	Decision Quality Instrument subscale "What Matters Most to You" adaptation	6/30/17
C2	Publish study protocol	Submission for publication of study protocol in peer review journal	6/30/17
C3	Outcome measures translated	Translation of study outcome measures into Spanish and Mandarin completed	8/31/17
C4	Study materials review by CAB	Preparation and review of all questionnaires and study materials by CAB and research team	8/31/17
C5	Recruitment begins	Enrollment begins for study participants (N=1,100)	9/30/17
C6	Follow-up data collection begins	Follow-up assessments begin for T2, T3, and T4	9/30/17
C7	DSMB meeting	DSMB meeting (occurs every six months until study completion) - submit meeting minutes with interim progress reports.	10/30/17
C8	Engagement Report	For each annual report (i.e., at year 1, year 2, etc. but not at 6 months or 18 months), additional descriptive information on engagement of patients and/or other stakeholders should be reported at https://live.datstatshost.com/PCORI-Collector/Survey.ashx?Name=Engagement_Report_Login . Confirmation code should be reported in the Engagement Report section of the PCORI interim progress report.	11/1/17
C	Progress Report Submission	Submit 12-month Interim Progress Report - use PCORI interim progress report template	11/1/17
D1	25% recruitment	Completion of 25% of study enrollment/recruitment (275/1100)	12/31/17
D2	25% follow-up data collection	Completion of 25% of follow-up data collection	3/30/18
D3	Begin interviews	Begin semi-structured interviews (Aim 3)	3/30/18
D4	50% recruitment	Completion of 50% of study enrollment/recruitment (300/600)	5/30/18
D5	DSMB meeting	DSMB meeting (occurs every six months until study completion) - submit meeting minutes with interim progress reports.	4/30/18
D6	Engagement Update	For the 6-month time intervals (i.e., 6 months, 18 months, 30 months, etc. but not at 12 months or 24 months), provide specific examples of the impact of engagement on project activities during the reporting period. Report this in the Engagement Report section of the PCORI interim progress report.	5/1/18
D	Progress Report Submission	Submit 18-month Interim Progress Report - use PCORI interim progress report template	5/1/18
E1	50% follow-up data collection	Completion of 50% of follow-up data collection	7/31/18
E2	75% recruitment	Completion of 75% of study enrollment/recruitment (450/600)	9/30/18
E3	One year post decision regret data and financial toxicity data collection begins	Begin collecting decision regret measure and financial toxicity (COST) one year post-decision for all women who received surgery in the first nine months of the trial.	10/30/18
E4	DSMB meeting	DSMB meeting (occurs every six months until study completion) - submit meeting minutes with interim progress reports.	10/30/18
E5	Engagement Report	For each annual report (i.e., at year 1, year 2, etc. but not at 6 months or 18 months), additional descriptive information on engagement of patients and/or other stakeholders should be reported at https://live.datstatshost.com/PCORI-Collector/Survey.ashx?Name=Engagement_Report_Login . Confirmation code should be reported in the Engagement Report section of the PCORI interim progress report.	11/1/18

E	Progress Report Submission	Submit 24-month Interim Progress Report - use PCORI interim progress report template	11/1/18
F1	75% follow-up data collection	Completion of 75% of follow-up data collection	11/30/18
F2	Completion of study enrollment	Completion of 100% of study enrollment/recruitment (600/600)	2/28/19
F3	One year post decision regret and financial toxicity data collection completed	Completion of collecting decision regret and financial toxicity measures one year post-decision for all women recruited in the first nine months of the trial.	5/31/19
F4	Completion of follow-up data collection	Completion of follow-up data collection	4/30/19
F5	Completion interviews	Completion of semi-structured interviews (Aim 3)	5/30/19
F6	DSMB meeting	DSMB meeting (occurs every six months until study completion) - submit meeting minutes with interim progress reports.	4/30/19
F7	Engagement Update	For the 6-month time intervals (i.e., 6 months, 18 months, 30 months, etc. but not at 12 months or 24 months), provide specific examples of the impact of engagement on project activities during the reporting period. Report this in the Engagement Report section of the PCORI interim progress report.	5/1/19
F	Progress Report Submission	Submit 30-month Interim Progress Report - use PCORI interim progress report template	5/1/19
G1	Final analyses	Final analyses completed	8/31/19
G2	Dissemination of findings	Dissemination of research findings	10/30/19
G3	Dissemination symposium	Dissemination symposium at each participating study site	10/30/19
G4	DSMB meeting	DSMB meeting (occurs every six months until study completion) - submit meeting minutes with interim progress reports.	10/30/19
G5	Engagement Report	For each annual report (i.e., at year 1, year 2, etc. but not at 6 months or 18 months), additional descriptive information on engagement of patients and/or other stakeholders should be reported at https://live.datstatshost.com/PCORI-Collector/Survey.ashx?Name=Engagement_Report_Login . Confirmation code should be reported in the Engagement Report section of the PCORI interim progress report.	11/1/19
G	Final Progress Report Submission	Submit Final Progress Report - use PCORI final progress report template	11/1/19
H	Research Project Period End Date		11/1/19
I	Primary Research Completion Date	A Primary Research Completion Date must be provided when registering the study in Clinicaltrials.gov. For studies that are not clinical trials or observational studies registered on ClinicalTrials.gov, the Awardee and PCORI shall agree on a primary completion date as a milestone that precedes the agreed-upon date to submit a Draft Final Research Report.	4/30/19
J	Results submitted to ClinicalTrials.gov or appropriate database.	Awardee ensures results are submitted to ClinicalTrials.gov or appropriate database. For ClinicalTrials.gov, the generated tables are a required section in the Draft Final Research Report.	4/30/20
K	Draft Final Research Report Submission	Submit Draft Final Research Report according to instructions found at http://www.pcori.org/awardee-resources *Draft Final Research Report must be submitted no later than 30 days from when results are posted to clinicaltrials.gov or other applicable website.	5/30/20
L	Final Research Report	Upon receipt of written summary, and as applicable, PI will make revisions and submit revised Draft Final Research Report for acceptance as directed by PCORI.	11/30/20
M	Approval / sign off of the Lay Abstract	Sign off must be no later than 90 days beyond the date PCORI accepts the final report	11/30/20
N	Contract Term Date	-	11/30/20

O	Final Expenditure Report	Submit Final Expenditure Report (See Contract for Instructions)	2/28/21
P	Notification of Publication Acceptance	See Contract for Instructions	Within 30 Days of Acceptance

7 Engagement Plan

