4.3.4 Feasibility of Recruitment

We aim to recruit 317 patients at Dartmouth-Hitchcock, Montefiore Medical Center, and Washington University in St. Louis (this number may vary depending on stratification and patient volume). Given the lower patient volume at NYU School of Medicine, we will aim to recruit 150 patients. At Dartmouth-Hitchcock, the screening exercise revealed that 339 women would have been eligible for participation in this study in 2014. This represents about 452 women potentially eligible over 18 months. At the Joanne Knight Breast Health Center (Washington University in St. Louis), 724 women would have been eligible to take part in the proposed study in 2014, representing approximately 965 eligible participants over 18 months. At Montefiore Medical Center, 443 women would have been eligible to take part in the proposed study in 2014. This represents a total of approximately 591 eligible participants over 18 months. Given a revised target sample size of 600 and varying recruitment by site, the per site enrollment will not reach these numbers, however we have accounted for this (see section 4.8 - Analysis).

Barriers to enrollment will be overcome by employing a research assistant and patient associate at each site throughout the study, by offering compensation for baseline and follow-up assessments, by informing participants of the study in advance of their surgical consultation, by developing materials with our patient and stakeholder partners using plain language and translations into Spanish and Mandarin Chinese, by offering several modes of questionnaire completion, and by working with our Community Advisory Board (see section

7.2 Conducting the Study for more detail on the Community Advisory Board) and patient and stakeholder partners to overcome potential issues with recruitment. We have allocated two extra months for the analysis and write-up of the findings, in case recruitment would need to be extended. We anticipate that the attrition rate will be minimal given the brevity of the trial, and will implement various strategies to maximize recruitment and retention.

Table 1. Recruitment Plan for the Randomized Controlled Trial

Estimated number of potentially eligible study participants	Based on administrative data: 2474
Total number of study participants expected to be screened	2400
Total number of study participants expected to be eligible	2200
Target sample size	600

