4.5 Outcomes

We have chosen outcome measures that are patient-centered and relevant to our target population with our patient and stakeholder partners. To accommodate varying levels of literacy and health literacy of our target group and to comply with patient partners' advice, we will use validated short-form questionnaires whenever possible. All patient and stakeholder partners have deemed the chosen measures important and relevant, highlighting their impact on patients' lives in both the short-term (e.g., treatment choice, anxiety) and longer-term (e.g., quality of life, decision regret). Aside from the Observer OPTION⁵ scale¹⁰², all are patient-reported outcome (PRO) measures. All included scales and tests are validated and have been developed and tested with patients. The demographic questions and item assessing the amount of out-of-pocket expenses incurred by the participant over the past month have not been validated.

We will measure outcomes at baseline (T0), during the clinic visit (T1), immediately after the visit (T2), one week post-surgery or around the first post-operative visit (T3) and 12 weeks post-surgery or around the second post-operative visit (T4). For all participants who receive surgery before May 2018, we will also measure decision regret and financial toxicity one year post-surgery (T5).

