4.7.6 Follow-up Assessments

During the clinic visit, we will audio-record clinical encounters with consented patients to assess the fidelity of intervention delivery (T1). After the visit, participants will be asked to complete a second questionnaire (T2). Two additional follow-up assessments will occur around 1-2 weeks (T3) and 12 weeks post- surgery (T4) (Fig. 5). For participants recruited in the first nine months of the trial, we will also conduct a follow-up assessment 1 year post-surgery (T5).

Follow up questionnaires will be administered in the clinic, when possible, and aligned with regularly scheduled return clinic visits. If this is not possible, follow-ups will be conducted either over the phone, online (sent as an email via REDCap), or on paper (sent via mail with a pre-stamped, self-addressed envelope).

To minimize respondent burden and disruption and to accommodate varying levels of literacy and health literacy, validated short-form questionnaires will be used. Each follow-up assessment (T2, T3, T4, and T5) comprises 10-34 items.

We expect that T0 (baseline assessment) will take between 15 and 30 minutes. All subsequent assessments will take approximately 10 minutes.

For each assessment, the outcome measures will be combined into one questionnaire to improve ease of use (see Table 4).

Table 4. Number of items according to data collection point

Measure	Number of Items	T0 Baseline	T2 Post-Visit	T3 1 Week Post-Surgery*	T4 12 Week Post-Surgery**	T5 1 Year Post-Surgery
Health literacy	1	X				
Demographic survey	6	X				
Decision quality	16		X	X		
Knowledge (5-item subscale of DQI)	5	X	(X)	(X)		

Treatment intention (self-reported)	1		(X)			
Quality of life	6	X			X	
Anxiety	8	X	X	X	X	
Shared decision-making (self-reported)	3		X			
Decision regret	5			X	X	X
Integration of healthcare delivery	4	X			X	
Financial toxicity	5			X	X	X
Total number of items		30	27	34	28	10

* or first post-operative visit

** or second post-operative visit

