4.8.7 Missing Data

Most data collection will be via online questionnaires (i.e., at T0, T2, T3, T4, and T5), which provide opportunities for preventing and monitoring missing data. We will offer other formats for questionnaire completion (including paper and standardized interviews), thus minimizing missing data. We will prompt each patient, by telephone (or email at Dartmouth), to complete the follow-up questionnaires (i.e., T3, T4, and T5) or reach them in the clinic during their post-surgery appointments. Given the brevity of the trial and the procedures described above, we do not anticipate more than 5% of missing data. However, should there be more than a trivial amount of missing data, we will use multiple imputation to cope with missing baseline, interim, and outcome data. We will record and report all reasons for dropout and missing data. Multiple imputation creates multiple completed data sets by drawing random values of missing outcome or predictor variables from the predictive distribution of these variables given the observed variables¹⁴². This approach will address both generalizability and causal validity bias. We will also examine sensitivity of inferences.

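### Table 5 closes follow-up 61 days after the last enrolment, but T4 is nominally 84 days after surgery, so a 12-week T4 does not fit for the last enrollees

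*Combined protocol and SAP*

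**What the plan says.** Section 6, Table 5 lists "Completion of 100% of study enrollment/recruitment (600/600") as milestone F2, dated 2/28/19, and "Completion of follow-up data collection" as milestone F4, dated 4/30/19. The Primary Research Completion Date (milestone I) is also 4/30/19. The follow-up that F4 closes was opened by milestone C6: "Follow-up assessments begin for T2, T3, and T4". T5 has its own milestones, E3 and F3.

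Section 4.7.6 places the post-surgical assessments "around 1-2 weeks (T3) and 12 weeks post- surgery (T4"). Section 4.5 gives T4 an alternative: "12 weeks post-surgery or around the second post-operative visit (T4"). The footnotes to Tables 3 and 4 repeat that alternative, and no day is given for the visit. Section 4.7.11 ends the study at 12 weeks after surgery for women without a T5, apart from any Aim 3 interview.

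Tables 3 and 4 schedule quality of life (EQ-5D-5L) and IntegRATE at T0 and T4 only. Section 4.8.7 says of missing data: "we do not anticipate more than 5% of missing data". Section 4.3.4 adds: "We have allocated two extra months for the analysis and write-up of the findings", as a reserve in case recruitment has to be extended.

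**The concern.** Surgery follows enrolment and T4 follows surgery by 12 weeks, so the gap between last enrolment and the end of follow-up should be at least 12 weeks plus the wait for surgery. Table 5 allows less than nine weeks. If the dates are applied as written, the last women enrolled either miss T4 or complete it early.

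Aim 1, Hypothesis 1 names both quality of life and perceived integration of care. For these two outcomes a missed T4 leaves no post-baseline value at all. An early T4 is less damaging, but the assessment would then come at a different stage of recovery for late enrollees than for everyone else, and the plan has no rule for handling that.

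Section 4.3.1 shows that the authors had this constraint in mind: women on neoadjuvant therapy are invited only in the first nine months, so that their follow-up can finish before the trial ends. No comparable provision covers other women enrolled late.

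**Working it through.** **Inputs from the documents**
- Last enrolment (F2): 2/28/19. Table 1 gives February 2018, which conflicts with the 18-month recruitment period in Section 4.1.1. F2 fits that period and is used here.
- End of T2–T4 follow-up (F4): 4/30/19.
- T4: 12 × 7 = 84 days after surgery.
- 75% recruitment (E2, 450/600): 9/30/18.
- Final analyses (G1): 8/31/19.

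**Assumption.** The documents give no interval from consultation to surgery. Waits of 0 to 6 weeks are shown.

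**Step 1: time allowed.** F4 − F2 = 61 days = 8.7 weeks. The shortfall against 84 days, with surgery on the day of enrolment, is 84 − 61 = 23 days.

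**Step 2: latest surgery date.** 4/30/19 − 84 days = 2/5/19. Later surgery puts a 12-week T4 after F4.

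**Step 3: late accrual rate.** From E2 to F2, 600 − 450 = 150 women are due in 151 days: 150/151 = 0.993 per day.

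**Step 4: women affected.** For a wait of w days, the 12-week T4 of the last enrollee falls on 2/28/19 + w + 84. The women affected are those enrolled in the last (23 + w) days, so their number is 0.993 × (23 + w).

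| Wait for surgery (assumed) | 12-week T4 of last enrollee | Days after F4 | Women affected | Share of 600 |
|---|---|---|---|---|
| 0 | 5/23/19 | 23 | 22.8 | 3.8% |
| 2 weeks | 6/6/19 | 37 | 36.8 | 6.1% |
| 4 weeks | 6/20/19 | 51 | 50.7 | 8.4% |
| 6 weeks | 7/4/19 | 65 | 64.6 | 10.8% |

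At the 40 per month in Table 1, the counts would be about 30, 49, 67 and 85.

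**Step 5: would another closing date help?** F3 (T5 completion) is 5/31/19, 92 days after F2. Even then only 92 − 84 = 8 days would remain for surgery. T5 also covers only decision regret and financial toxicity, in early participants.

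**Step 6: which outcomes are exposed?**
- EQ-5D-5L and IntegRATE (T0, T4) have no other post-baseline point.
- Anxiety is also measured at T2 and T3, and regret and financial toxicity at T3.
- DQI is measured at T2 and T3. A one-week T3 fits for surgery up to 4/30/19 − 7 days = 4/23/19, which is 54 days after the last enrolment.

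**Step 7: comparison within Table 5.** The gaps from recruitment milestone to matching follow-up milestone are 89 days at 25% (D1 to D2), 62 at 50% (D4 to E1), 61 at 75% (E2 to F1) and 61 at 100% (F2 to F4). The first exceeds 84 days. The shorter gaps begin at the first milestone restated for 600 women (D4). Follow-up dates may not have been moved with recruitment, but that is an inference.

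**The case against.** The strongest reply is that Section 4.5 and the table footnotes let T4 be done around the second post-operative visit. If that visit comes well before 12 weeks, some late enrollees could complete T4 by 4/30/19. This stands: the impossibility holds only for a T4 at 12 weeks. It does not remove the problem, because T4 timing would then depend on when a woman was enrolled.

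Second, Table 5 gives projected dates, and nothing says that a T4 form arriving after F4 will be refused. Section 4.7.11 ties the end of participation to surgery, not to the calendar. Interviews run to 5/30/19 and T5 to 5/31/19. A reader might infer that T4 data from 23 to 65 women will be lost; the documents do not show that. They show dates that conflict with the assessment schedule, and a loss that would follow if those dates were enforced.

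Third, a reader might set 4% to 11% against the 5% in Section 4.8.7 and conclude that a limit is breached. That figure is an expectation, not a maximum. The same section provides for multiple imputation, and Section 4.8.1 assumes 20% attrition. Even so, imputation is a poor substitute for planned data that a change of date would capture.

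Fourth, a reader might infer that Aim 3 is at risk because its interviews follow T4. Section 4.3.3 needs a purposive sample of 60 participants, and Table 5 starts interviews on 3/30/18, so Aim 3 does not depend on the last enrollees.

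**Conclusion.** The point holds as a scheduling inconsistency with consequences for secondary outcomes. F4 falls at least 23 days before the last enrollees can reach a 12-week T4. The least number affected is about 23 of 600 (4%); it assumes even accrual between E2 and F2 and surgery on the day of enrolment. The larger counts, up to about 65 (11%) at six weeks, rest on assumed waits. Any positive wait widens the gap.

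The exposure is mainly EQ-5D-5L and IntegRATE. Anxiety, regret and financial toxicity would lose one time point but keep T3. The finding does not threaten the primary analysis: T2 is completed straight after the consultation, and a one-week T3 fits within F4 for every wait considered here.

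**What to change.** Reconcile F2, F4 and the T4 definition by moving F4 to at least 12 weeks plus the expected wait for surgery after the last enrolment. That is no earlier than 5/23/19, and 6/20/19 to 7/4/19 for a 4- to 6-week wait. State the wait that was assumed. Move the Primary Research Completion Date only if it is meant to cover T4. F5 (completion of interviews) need not move.

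If F4 has to stay, either end enrolment earlier or state how T4 data that are early or arrive after F4 will be handled.

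The cost is a milestone amendment and less time for analysis. The interval from F4 to final analyses (8/31/19) is now 123 days. It would fall to 72 days (F4 at 6/20/19) or 58 days (F4 at 7/4/19), about two months less. Section 4.3.4 already reserves two extra months for analysis and write-up, and field staff are already collecting other data until late May.
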